10.3. Adverse event reporting

Serious and non-serious events (expected or unexpected) will be reported to the IRB within specific timelines depending on the severity of the event. Serious adverse events will be reported within 15 calendar days of receipt, whereas non-serious adverse events will be reported on a periodic basis.

All the adverse event forms will be kept in the corresponding study records of adverse events, including any follow-up actions taken, for a period of time as specified by the regulatory agency.

10.4. Calculation of the sample size

The calculation of the number of patients to demonstrate a positive effect for the use of peripheral blood transcriptomics for the diagnosis of the presence of severe coronary calcification is carried out based on previous experiences by the group of researchers. There is still no standardized methodology in the medical literature to perform the sample calculation of this type of analysis, since it is very recent and is in the exploration phase. *In silico* studies carried out by this group of researchers and the preliminary clinical studies carried out previously showed that at least a sample of 150 patients is necessary for the initial training of the artificial intelligence algorithm that detects transcriptional differences between patients with or without a solid tumor. (for example, breast tumor). Therefore, 200 patients will be included based on the minimum number necessary to perform the initial training of an artificial intelligence algorithm.

10.5. Analysis plan

For the description of the general characteristics of the study population, descriptive statistics such as means, medians and proportions will be used. To calculate the diagnostic performance of the method, the following will be calculated:

- True Positives (TP) or the probability that the test is positive since the disease is present
- True Negatives (TN) or the probability that the test is negative since the disease is not present.
- False Positives (FP) or Type I Error
- False Negatives (FN) or Type II Error
- Sensitivity: $VP/VP+FN$
- Specificity: $VN/ VN+FP$
- Precision or accuracy: $VP/VP+FP$ or sensitivity + (1-specificity)

The accuracy can vary between 0.5 and 1, where 1 represents a perfect diagnostic value and 0.5 is a test without diagnostic discriminatory capacity. An area under the curve (AUC) will also be performed to determine the diagnostic capacity of the trained algorithm.

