6.1 Primary Objective

The main objective of this study is to investigate the diagnostic accuracy of whole-blood transcriptome analyzed by artificial intelligence in detecting the presence and extent of coronary atherosclerosis in stable patients with suspected or known coronary artery disease (CAD), using coronary computed tomography angiography (CCTA) images.

Specific aims:

I) To classify patient transcriptomes based on the presence and extent of the following CCTA outcomes:

- Coronary calcium score
- Total coronary plaque burden
- Degree of coronary stenosis
- Coronary high-risk plaques (low-attenuation, positive remodeling; spotty calcification, or napkin-ring sign)

II) To train artificial intelligence algorithms using information from the transcriptome to recognize the outcomes of interest in the training set.

III) To explore the diagnostic accuracy (sensitivity and specificity) of the method in detecting the presence, absence, or extent of the outcomes of interest in the validation/test set.

6.2 Secondary Objectives:

The secondary objectives of this study are as follows:

6.2.1 To explore the diagnostic accuracy of whole-blood transcriptome in relation to other outcomes of interest provided by CCTA images, including:

- Presence and extent of aortic calcification
- Hepatic steatosis
- Flow limiting artery obstruction (coronary fractional flow reserve)
- Coronary artery inflammation (perivascular fat attenuation index)
- Total epicardial adipose tissue volume

6.2.2 To calculate the polygenic risk score (PRS) from the transcriptome and explore its association with the previously described outcomes of interest.

6.2.3 To explore the differences in transcriptomics of peripheral blood between patients who did and did not develop a cardiovascular event during follow-up.

7. Methods

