9.5. Analysis of Coronary Computed Tomography Angiography

Coronary Calcium scoring will be analyzed using dedicated software (HeartBeat-CS, Philips Healthcare, Best, The Netherlands) by an experienced observer blinded to the clinical characteristics, laboratory, and transcriptome results. The presence of CAC and its extension will be evaluated using both ordinal variables (number of segments with CAC and number of affected vessels, and qualitatively: absence, mild, moderate, and severe) and continuous variables (Agatston units). The presence and extension of calcifications at the level of the aortic valve and the thoracic aorta (Agatston units) will also be evaluated independently. The extent of aortic calcification will be evaluated in sections that include the area ranging from the bifurcation of the pulmonary artery as the upper limit to the diaphragm as the lower limit.

CCTA images will be anonymised locally and transferred to a core laboratory located in Oxford, UK, for analysis of secondary outcomes by investigators who will be unaware of population demographics and outcomes. The presence of obstructive CAD will be defined as the presence of at least one lesion causing a luminal stenosis of 50% or larger. The extent of coronary artery disease using the modified Duke coronary artery disease index, as follows (Group 1: <50% stenosis; Group 2: ≥ 2 mild stenosis with proximal CAD in 1 artery or 1 moderate stenosis; Group 3: 2 moderate stenosis or 1 severe stenosis; Group 4: 3 moderate stenosis, 2 severe stenosis, or severe stenosis in the proximal left anterior descending (LAD) artery; Group 5: 3 severe stenosis or 2 severe stenosis in the proximal LAD; Group 6: $\geq 50\%$ stenosis in left main coronary artery). The presence of high-risk plaque features (spotty calcification, low-attenuation plaque, positive remodeling, and napkin-ring sign) will be explored. The total epicardial adipose tissue volume will be calculated in a semi-automated manner by tracking the contour of the pericardium from

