the level of the pulmonary artery bifurcation to the apex of the heart at the most caudal end. To measure the perivascular FAI, we will trace the proximal 40-mm segments of all three major epicardial coronary vessels (right coronary artery, left anterior descending artery, and left circumflex artery) and defined respective perivascular fat as the adipose tissue within a radial distance from the outer vessel wall equal to the diameter of the vessel, as described and validated previously. To avoid the effects of the aortic wall, we excluded the most proximal 10 mm of the right coronary artery and analyzed the proximal 10–50 mm of the vessel, as described previously. In the left anterior descending artery and left circumflex artery, we will analyze the proximal 40 mm of each vessel.

As follows, 3-dimensional plaque quantification of the whole vessel will be performed (10,13) using semi-automated plaque analysis software. All IDs will undergo double reading of the main outcome of the study (presence or extent of CACs). This reading will be carried out by an expert external to the group of researchers of the study and blind to the first reading. In case of disagreement, consensus will be sought between the two experts. The aim of this process is to enhance the internal validity of the study.

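### Extent of coronary disease is part of the primary objective, but section 10.5 plans only present/absent metrics and an AUC, with no calcium cut-off

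*Protocol*

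**What the plan says.** Protocol 6.1 sets the primary objective as diagnostic accuracy "in detecting the presence and extent of coronary atherosclerosis in stable patients". Specific aim I applies presence and extent to calcium score, plaque burden, stenosis and high-risk plaque. Specific aim III names the performance measures: "To explore the diagnostic accuracy (sensitivity and specificity) of the method in detecting the presence, absence, or extent of the outcomes of interest".

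Protocol 9.5 arranges a blinded double reading of the "main outcome of the study (presence or extent of CACs". It records calcium both as "continuous variables (Agatston units" and in ordinal form: counts of segments and vessels, and "qualitatively: absence, mild, moderate, and severe". It adds "The extent of coronary artery disease using the modified Duke coronary artery disease index", which has six groups, and three-dimensional plaque quantification.

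Protocol 10.5 introduces its metrics with "To calculate the diagnostic performance of the method, the following will be calculated". The list is true positives, true negatives, false positives, false negatives, sensitivity, specificity and a precision or accuracy figure, and an AUC follows. The true-positive and true-negative entries are defined by the disease being present or not. The section has no correlation, agreement, ordinal or prediction-error measure.

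On cut-offs, 9.5 defines obstructive disease by a 50% stenosis. No Agatston value separates the four calcium grades, and the severe calcification mentioned in 10.4 is not defined.

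**The concern.** Half of the primary question is graded: how much disease does the patient have? The imaging section spends effort on measuring that on continuous and ordinal scales, yet the planned metrics use only a yes/no version of it. A sensitivity for extent has no meaning until someone says which extent counts as positive, and for calcium the protocol does not say.

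Two things are at stake. The first is information: a cut treats a patient just above it and a patient far above it as the same. The second is the freedom to choose. If the calcium cut-offs are fixed only after models have been trained, they can be chosen where the algorithm performs best.

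**Working it through.** **Reproducing the plan's figure.** The protocol states no information loss, prevalence, distribution or calcium cut-off, so there is no figure of its own to reproduce. Its only design number is the 200 patients in 10.4, given without alpha, power or effect size. The point does not depend on it.

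**Objective against metrics.**

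| Extent outcome (9.5) | Scale | Extent measure in 10.5 | Cut-off given |
|---|---|---|---|
| Agatston score | continuous | none | no |
| Calcium grade | 4 ordered levels | none | no |
| Plaque quantification | continuous | none | no |
| Modified Duke index | 6 ordered groups | none | groups defined, no binary split |

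**What one cut costs.** Assume that extent, suitably transformed, is normal. Let p be the share of patients called positive, z the matching normal quantile and φ the normal density. The information kept, relative to the full scale, is φ(z)² / [p(1−p)].

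- p = 0.5: 0.3989² / 0.25 = 0.637, a loss of 36%.
- p = 0.2: 0.2800² / 0.16 = 0.490, a loss of 51%.
- p = 0.1: 0.1755² / 0.09 = 0.342, a loss of 66%.
- p = 0.05: 0.224 kept, a loss of 78%.

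**If many calcium scores are zero.** Assume half are zero, with a normal scale underneath. The full score then carries 0.5 × 0.798² + 0.5 = 0.818 of the underlying information. Cutting at any versus none keeps 0.637 / 0.818 = 0.78, a loss of about 22%. With 30% zeros the full score carries 0.921, and a cut at the top 10% keeps 0.342 / 0.921 = 0.37, a loss of 63%. A simulation of two million patients agreed with both figures. Over the cuts tried with 30% or 50% zeros, the loss ran from 22% to 63%.

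**If four ordered levels are kept.** The information kept is the sum over levels of pᵢmᵢ², where mᵢ is the mean normal score in level i. Equal quarters keep 0.861; a 40/30/20/10 split keeps 0.834; a 50/25/15/10 split keeps 0.788. The loss is therefore about 14% to 21%, well below that of a single cut in most cases.

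**What the AUC does and does not see.** Suppose a score separates only the top and bottom 20% of patients and is random among the middle 60%. At a median cut, half the positives' ordering is decided as follows: a pair is uninformative only if both members fall in the middle, so the AUC is 1 − 0.5 × 0.6 × 0.6 = 0.82. With 30% positive it is 1 − 0.5 × (1/3) × (5/7) = 0.88. With 20% positive it is 1.00. A score that orders everyone perfectly has 1.00 throughout. The AUC therefore distinguishes the two scores at some cuts and not at others, and which applies depends on the unstated cut-off.

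**The case against.** The strongest reply is that 10.5 does what specific aim III asks. That aim itself assigns sensitivity and specificity to extent, aim I speaks of classifying, and 10.4 treats severe calcification as a state that is present or absent. This stands: section 10.5 is faithful to aim III. It moves the mismatch rather than removing it, because aim III also gives no calcium cut-off.

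Second, the listed metrics can be reported per class or at each threshold of the four grades or six groups, and the laboratory already shows multi-class confusion matrices (5.1). This also stands. A reader might infer that every graded outcome must become a single yes/no split, or that half of the primary objective cannot be answered. The protocol does not force either. It simply does not say which route will be taken.

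Third, a reader might take a loss of one third to two thirds as a property of this study, or quote power for 200 patients. Neither is supported. The loss depends on an assumed distribution, number of cuts and prevalence. Performance is to be judged in the validation/test set, not in all 200. If the 10% to 20% validation share described in 5.1 applied here, that set would hold 20 to 40 patients.

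Fourth, it would be wrong to say that good ordering earns no credit, since the AUC uses ranks.

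Finally, 10.5 does not call its list exclusive, and a separate analysis plan may add extent measures. That limits the point to a mismatch within the protocol; it does not make the sections agree.

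**Conclusion.** The point holds in limited form. Sections 6.1 and 9.5 make extent part of the primary objective and main outcome, while aim III and 10.5 evaluate it only with two-state metrics and without a calcium cut-off. Followed as written, extent is either not assessed as extent or is collapsed at cut-offs still to be chosen.

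The single-cut losses assume a normal scale, and the smaller losses assume a mass of zero scores or four retained levels. Because the protocol supplies none of these inputs, all the figures are illustrative and no single one should be quoted as the loss in this study. The binary metrics are not wrong in themselves and the study is not invalidated. This is a cheap improvement.

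**What to change.** In 10.5, add for the extent outcomes:

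- a Spearman correlation between predicted and observed Agatston score, and likewise for plaque volume;
- a quadratically weighted kappa or an ordinal c-index for calcium grade and for Duke group;
- a 95% confidence interval for each, calculated in the validation/test set.

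Keep sensitivity, specificity and AUC both for presence and for extent thresholds such as severe calcification, and state those cut-offs before model training. Restricting these metrics to presence outcomes would conflict with aim III and with the target in 10.4. Align the wording of aim III with the expanded list.

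The cost is a few lines of text and slightly more output from data already being collected. The intervals will be wide in a small test set. On the Fisher z scale the half-width for a correlation is roughly 1.96/√(n−3), which is 1.96/√37 = 0.32 for 40 patients and 1.96/√17 = 0.48 for 20. Those set sizes assume the 20% and 10% shares in 5.1. The added measures should be presented as estimates with that uncertainty shown.

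### Section 10.5 defines precision or accuracy by two unequal formulas, and the second gives a perfect test and a coin flip the same value

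*Protocol*

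**What the plan says.** Section 10.5 lists the measures of diagnostic performance. VP and VN are evidently the true positives and true negatives that the same list abbreviates as TP and TN.

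- The cells are described as probabilities or error types, for example "True Positives (TP) or the probability that the test is positive since the disease is present" and "False Positives (FP) or Type I Error".
- Sensitivity and specificity follow: "Sensitivity: $VP/VP+FN" and "Specificity: $VN/ VN+FP".
- One entry then covers two measures: "Precision or accuracy: $VP/VP+FP$ or sensitivity + (1-specificity)".
- The next sentence gives the scale: "The accuracy can vary between 0.5 and 1, where 1 represents a perfect diagnostic value and 0.5 is a test without diagnostic discriminatory capacity".
- The AUC comes last, as an additional measure: "An area under the curve (AUC) will also be performed to determine the diagnostic capacity of the trained algorithm".

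In Section 6.1, specific aim III names the measures of interest: "To explore the diagnostic accuracy (sensitivity and specificity) of the method". No other section defines accuracy or corrects the entry in Section 10.5.

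**The concern.** Precision (the positive predictive value, PPV) and accuracy (the proportion correctly classified) are different measures. The entry treats them as one and offers two formulas as if they were interchangeable. They are not equal, and the second is neither measure. It adds the false-positive rate to the true-positive rate, so false positives count in the test's favour. It therefore cannot carry the scale stated in the next sentence.

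The first formula is ambiguous. It is normally computed from patient counts, but Section 10.5 describes its terms as a conditional probability and a Type I error. The two readings give different results.

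Diagnostic accuracy is the subject of the primary objective. A reader who meets a figure labelled precision or accuracy could not tell which quantity it is. If the second formula were used, a worse classifier could be reported with a higher value, and a value of 1 could be misread as perfect.

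**Working it through.** **Inputs.** The formulas and the 0.5 to 1 scale are from Section 10.5. The total of 200 patients is from Section 10.4; it only scales the example tables and cancels out of every ratio. The protocol gives no prevalence, so 20% is assumed for illustration, with a range of 10% to 50%. The printed ratios lack parentheses, and the evident ones are supplied, for example VP/(VP+FP). Write Se for sensitivity, Sp for specificity and p for prevalence.

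**Second formula: Se + (1 − Sp).** No prevalence is needed.

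- Perfect test: 1 + 0 = 1.0
- Se = Sp = 0.90: 0.90 + 0.10 = 1.0
- Coin flip: 0.5 + 0.5 = 1.0
- Always positive: 1 + 1 = 2.0
- Always negative: 0 + 0 = 0
- Random rule calling a fraction q positive: Se = q and Sp = 1 − q, so the value is 2q
- Se = 0.80, Sp = 0.90: 0.80 + 0.10 = 0.90, which is below the coin flip

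The plan's scale is not reproduced. Its two ends, no discrimination and perfect, can receive the same value, and the range is 0 to 2.

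**First formula, terms as Section 10.5 describes them.** TP is then Se and FP is 1 − Sp, so the formula is Se/(Se + 1 − Sp). A perfect test gives 1/(1 + 0) = 1.0 and a random rule gives q/(q + q) = 0.50. These match the stated anchors. However, the result equals the cohort's PPV only at 50% prevalence, and it is not the proportion correctly classified.

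**First formula, terms as patient counts.** The formula is then PPV = TP/(TP + FP). At p = 0.20 there are 40 diseased and 160 non-diseased patients. With Se = 0.80, TP = 32 and FN = 8.

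| Sp | FP | TN | PPV | Accuracy (TP+TN)/200 | Se/(Se+1−Sp) | Se+(1−Sp) |
|---|---|---|---|---|---|---|
| 0.80 | 32 | 128 | 32/64 = 0.50 | 160/200 = 0.80 | 0.80/1.00 = 0.80 | 1.0 |
| 0.60 | 64 | 96 | 32/96 = 0.33 | 128/200 = 0.64 | 0.80/1.20 = 0.67 | 1.2 |
| 0.40 | 96 | 64 | 32/128 = 0.25 | 96/200 = 0.48 | 0.80/1.40 = 0.57 | 1.4 |

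As specificity falls, every measure in the table falls except the second formula, which rises.

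The PPV of an uninformative test equals the prevalence: 0.10, 0.20 and 0.50 at p = 0.10, 0.20 and 0.50. For Se = Sp = 0.80, the PPV is 16/(16 + 36) = 0.31 at p = 0.10 and 80/(80 + 20) = 0.80 at p = 0.50.

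**The scale and true accuracy.** The proportion correctly classified does not follow the 0.5 to 1 scale either. At p = 0.20, calling every patient negative is correct for 160/200 = 0.80 without discriminating at all. The scale sentence would therefore still be misplaced if accuracy were defined correctly.

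**Lines that are unaffected.** On the probability reading, sensitivity is Se/(Se + 1 − Se) = Se, and specificity likewise returns Sp. Both lines are correct on either reading.

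**The case against.** The strongest objection is about weight. Aim III in Section 6.1 specifies sensitivity and specificity, Section 10.5 defines both correctly, and the AUC is listed as well. The study is exploratory, and no sample size or decision rule uses this entry. That stands, and it limits the finding to one summary measure.

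A second objection is that the line is loose drafting. It mixes TP/TN with VP/VN, omits parentheses, and may be a garbled reference to ROC analysis, whose axes are sensitivity and 1 − specificity. That is plausible, and it makes real use of the second formula less likely. It does not make the text right, because the AUC is introduced afterwards as an additional measure. Simple repairs of the expression do not help either. Halving it gives 0.5 for both the perfect test and the coin flip. Changing the plus to a minus gives Youden's index, which is 0 for a coin flip. Changing it to a division gives a likelihood ratio, which is 1 for a coin flip and unbounded for a perfect test.

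Third, the quantity Se/(Se + 1 − Sp) arises only if the cell descriptions are taken literally and not as loose glosses. That is fair. Without it, the two printed formulas are still unequal and the second still contradicts the scale.

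Finally, the intended home of the 0.5 to 1 scale is an inference. Balanced accuracy, (Se + Sp)/2, has the same anchors as the AUC. The authors should confirm which they meant.

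A separate statistical analysis plan would not remove the problem, since the protocol prints a wrong formula and does not merely leave out a detail.

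**Conclusion.** The concern holds. The entry joins two measures under one label with two unequal formulas. The second is neither measure, and it contradicts the scale in the next sentence. This part needs no assumption: the value is 1.0 for a perfect test and for a coin flip, the range is 0 to 2, and it rises from 1.0 to 1.4 as specificity falls from 0.80 to 0.40 with sensitivity held at 0.80.

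On neither reading does the first formula give accuracy. One test with sensitivity and specificity of 0.80 can therefore appear as 1.0, 0.80 or 0.50. The 0.50 rests on the assumed 20% prevalence, and over an assumed 10% to 50% that PPV runs from 0.31 to 0.80.

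The entry should be corrected, but the effect is modest. Sensitivity, specificity, the AUC and the sample size are untouched.

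**What to change.** In Section 10.5:

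1. Define TP, TN, FP and FN as numbers of patients, use one set of abbreviations throughout, and add the missing parentheses.
2. Delete the formula that adds sensitivity and 1 − specificity.
3. List two separate measures: precision (PPV) = TP/(TP + FP), and accuracy = (TP + TN)/(TP + TN + FP + FN).
4. Attach the 0.5 to 1 sentence to the AUC. If the authors meant balanced accuracy, name it and define it as (Se + Sp)/2.

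The cost is a few lines of wording. No new data are needed, and the sample size, sensitivity, specificity and AUC do not change.

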10.6. Control of good clinical practices

The proposed study will be conducted following the recommendations of the International Council for Harmonization (ICH) for clinical studies (E6R2) (*ICH Official Web Site : ICH, nd*). In particular, the control of good clinical practices will be supervised in those elements that concern this type of evaluation study of new technologies, including patient confidentiality and informed consent. In addition, the standards suggested by the same regulations will be met (E18, (*ICH Official Web Site : ICH, nd*))⁴⁴.

⁴⁴ "Efficacy Guidelines - ICH." <https://www.ich.org/page/efficacy-guidelines>. Accessed 10 Apr. 2023.

All study investigators have been certified in GCP guidelines. New study personnel will also be required to obtain this certification.

